6.4.2 Criteria and procedure for premature withdrawal of a participant from the study

- Subjects may exit the study at any time and for any reason.
- The investigator can temporarily or permanently withdraw a subject from the study for any safety reason or if it is in the subject's best interests.
- Subject lost to follow-up: the subject cannot be located. The investigator must make every effort to reconnect with the subject (and record his attempts in the source file), at least to determine whether the subject is alive or dead

If a subject exits the trial prematurely or withdraws consent, any data collected prior to the date of premature exit may still be used.

The case report form must list the various reasons why the subject exited or was withdrawn from the study:

- Lack of efficacy
- Adverse reaction
- Other medical problem
- Subject's personal reasons
- Explicit withdrawal of consent
- Lost to follow-up
- Death

- ***Treatment stopping rules:***

Each investigator is strongly encouraged to stop administration of the product before the end of the treatment if any of the following events occurs, in the **absence of a clear underlying cause other than treatment administration:**

- Serious bleeding event (necessitating the transfusion of more than 4 packed red cells) in the absence of any invasive procedure.
- Severe diffuse intravascular coagulation, with QT a ratio <20%
- Severe liver cytolysis, with AST and ALT above 10 times normal
- Severe leucopenia (<500 G/L)
- Severe allergic reaction (anaphylactic shock, angio-edema, bronchospasm, severe skin reaction) at the time of or following drug injection
- Severe cardiac arrhythmia at the time of drug injection

6.4.3 Follow-up of participants following premature withdrawal from the study

If a subject exits the trial this will in no way affect the standard care received for his/her condition.

In case of severe adverse events, the investigator must notify the sponsor and monitor the subject for 3 months following the premature termination of treatment. If treatment is stopped prematurely

due to a serious adverse event, a serious adverse event report will be sent by mail ([contact]) to the sponsor. The serious adverse reaction will be monitored until it is resolved.

6.4.4 Procedures for replacing participants

Subjects exiting the trial will not be replaced. They will receive further standard usual care, and their data will be analysed with intent to treat analysis according to their group of randomization.

6.4.5 Full or partial discontinuation of the study

AH-HP (the sponsor) or the Competent Authority (ANSM) may prematurely discontinue all or part of the trial, temporarily or permanently, upon the recommendation of the Data Monitoring Committee in the following situations:

- first, if suspected unexpected serious adverse reactions (SUSARs) are observed in one of the treatment arms or if there is a discrepancy in the serious adverse reactions between the two treatment arms, requiring a reassessment of the benefit-risk ratio for the trial.
- similarly, AH-HP, as the sponsor, or the Competent Authority (ANSM) may prematurely cancel the trial due to the discovery of unexpected facts or new information about the product, in light of which the objectives of the study or clinical programme are unlikely to be achieved.
- AP-HP, as the sponsor, reserves the right to permanently suspend enrolment at any time if the enrolment targets have not been met.

If the study is cancelled prematurely, AP-HP will inform the Competent Authority (ANSM) and the Institutional Review Board of its decision within 15 days, together with justification for the decision and any recommendations from the Data Monitoring Committee (if applicable). Subjects will receive further standard usual care and will be followed until the end of the study, i.e. 3 months.

7 TREATMENT ADMINISTERED TO STUDY PARTICIPANTS

7.1 Description of the investigational medicinal product(s)

7.1.1 Investigational medicinal product 1

Investigational medicinal product n°1: FX06

FX06, a drug arising from research on fibrin-derived peptide B β 15-42, is able to stabilize VE-cadherin dependent cell-cell interactions, thereby reducing vascular leak [9,10]. The treatment will be administered as soon as possible after randomization, but no longer than 12 hours.

FX06 80 mg/ml solution for injection and its placebo will be supplied as clear, colorless single-use glass vials containing 2.75 ml ready-to-use solution, closed with a rubber stopper and aluminum flip-off cap. Each Therapeutic Unit will contain 10 vials.

Treatments will be stored in each ICU in a secured refrigerator, under the supervision of the pharmacy department of each center. The trial medication should be stored at 2–8°C in a secured refrigerator. After storage at 4°C, FX06 80 mg/ml was stable for 24 months.

Composition of FX06 ready to use vials

Ingredient	Function
Peptide B β ₁₅₋₄₂	Active ingredient
Disodium hydrogen phosphate, 0.118 mg/ml anhydrous	Buffer
Sodium dihydrogen phosphate, 1.265 mg/ml monohydrate	Buffer

Ingredient		Function
Sodium chloride	4.48 mg/ml	
Water for injection	ad 2.75 ml *	Diluent

* to ensure 2.5 ml retractable volume

The following dosing schedule will be used:

I.V. 200 mg starting dose as a bolus followed by a second bolus of 200 mg 10-15 min later i.v. during 5 days.

	Patient 1	Patient 2	Patient 3	etc
Day 1	2.5 ml	2.5 ml	2.5 ml	
	Wait 10-15 min	Wait 10-15 min	Wait 10-15 min	
	2,5 ml	2,5 ml	2,5 ml	
Day 2	2.5 ml	2.5 ml	2.5 ml	
	Wait 10-15 min	Wait 10-15 min	Wait 10-15 min	
	2,5 ml	2,5 ml	2,5 ml	
Day 3	2.5 ml	2.5 ml	2.5 ml	
	Wait 10-15 min	Wait 10-15 min	Wait 10-15 min	
	2,5 ml	2,5 ml	2,5 ml	
Day 4	2.5 ml	2.5 ml	2.5 ml	
	Wait 10-15 min	Wait 10-15 min	Wait 10-15 min	
	2,5 ml	2,5 ml	2,5 ml	
Day 5	2.5 ml	2.5 ml	2.5 ml	
	Wait 10-15 min	Wait 10-15 min	Wait 10-15 min	
	2,5 ml	2,5 ml	2,5 ml	

400 mg i.v. was the dose used in the FIRE trial [5], and the regiment chosen for the study close to the one used as rescue therapy during EBOLA-induced ARDS [6]. In addition, 6 Covid-19 patients were treated with FX06 as rescue therapy in Frankfurt and Würzburg, Germany up to 7 days (400mg/ day). Four over six patients could improve their condition, while 2 died. No clear adverse event related to the treatment could be detected in this cohort (data submitted for publication).

FX06 and its placebo will be supplied by MChE Handelsges.m.b.H (F4-Pharma) and delivered in each ICU under supervision of the local Pharmacy department of each hospital.

7.1.2 Investigational medicinal product 2

Placebo will be provided also as ready to use vials, containing the vehicle of FX06 drug product, i.e., phosphate-buffered saline. The same packaging as for FX-06 drug will be used for the placebo. The composition is given in the table below

Composition of placebo

Ingredient		Function
Disodium hydrogen phosphate, anhydrous	0.118 mg/ml	Buffer
Sodium dihydrogen phosphate, monohydrate	1.265 mg/ml	Buffer
Sodium chloride	4.48 mg/ml	
Water for injection	ad 2.75 ml *	Diluent

* to ensure 2.5 ml retractable volume

Treatments will be stored in each ICU in a secured refrigerator, as for the treatment.

7.2 Description of Additional medicinal product(s) (treatments required to conduct the study)

None

7.3 Description of traceability elements accompanying the investigational medicinal product(s)

Inclusion and exclusion criteria will be verified by each investigator before inclusion, using a web based questionnaire.

Study treatment will be supply by MChE Handelsges.m.b.H (F4-Pharma). As the Therapeutic units contain 10 vials, In order to track the treatment given to each patient, all the information related to the treatment will be collected on a traceability sheet (Preparations, date and time of administration, Therapeutic Unit number...).

7.4 Authorised and prohibited treatments (medicinal, additional medicinal, surgical), including rescue medications

Adjunctive therapy against COVID-19: As researches are evolving quickly, a specific treatment against SARS-CoV-2 virus will be authorized, as soon as it is clearly stated in a written policy for the hospital center. Particularly, dexamethasone (oral or intravenous) 6 mg daily for up to 10 days or until discharge if sooner will be strongly encouraged, regarding the data from RECOVERY trial (<https://www.medrxiv.org/content/10.1101/2020.06.22.20137273v1>). Immunosuppressive drugs or monoclonal antibody therapy targeting the inflammation process will not be authorised.

Standard usual care will be provided in both groups:

- **Management of ARDS** will follow last recommendations from the French society of intensive care (SRLF-Société de réanimation de langue française): <https://www.srlf.org/rfe-srlf-prise-en-charge-du-syndrome-de-detresse-respiratoire-aigue-sdra-de-ladulte-a-la-phase-initiale/>
 - o Tidal volume will be set at 6 ml/kg of ideal body weight
 - o Pplat will be monitored continuously, and kept ≤ 28 cmH₂O
 - o PEEP (positive end-expiratory pressure) will be the highest to reach a plateau pressure of 28 cmH₂O
 - o Neuromuscular blockers will be added during 48h in case of PaO₂/ FiO₂ ratio below 150 mmHg, and reevaluated afterwards
 - o Prone positioning (≥ 16 hrs) will be encouraged if the PaO₂/ FiO₂ ratio is below 150 mmHg
 - o Contact with an ECMO center will be encouraged in case of a PaO₂/ FiO₂ ratio below 80 mmHg or impossibility to maintain a protective mechanical ventilation, despite those measures
 - o CO₂ removal devices will be discouraged
 - o Nitric oxide administration will be discouraged
- Administration of fluids will be protocolized during the first 72h

Crystalloids will be allowed in case of circulatory failure with signs of pre-load dependence. The solution used will be NaCl 0.9%, and ringer lactate encouraged after 2 liters.

- Packed red cells will be allowed if Hb<7g/dl or active bleeding. Fresh frozen plasma if thromboplastin time ratio<20% or if severe bleeding.
- Platelets will be allowed if <30 G/L or in case of severe bleeding.
- Albumin will not be allowed, as its efficacy is not demonstrated in this pathology, and neither in a large randomized trial in SIRS associated with sepsis [17].
- Adjunctive hydrocortisone and fludrocortisone will be discouraged, as its efficacy has not been demonstrated to date in this pathology.

7.5 Methods for monitoring compliance with the treatment

Treatment actually administered to the patient will be assessed by the investigator at the end of the perfusion and recorded in the e-CRF.

8 EFFICACY ASSESSMENT

8.1 Description of efficacy endpoints assessment parameters

Extravascular lung water index (EVLWi) measured by transpulmonary thermodilution. See par 4.1

8.2 Anticipated methods and timetable for measuring, collecting and analysing the efficacy data

EvLWi recorded between D1 and D7. See par 5.5

9 SPECIFIC STUDY COMMITTEES

NB: the Data Safety Monitoring Board (DSMB) is described in Safety section.

9.1 Steering Committee

- Members of the committee:
 - [name] (Coordinating investigator)
 - Project manager URC et DRCI (sponsor's appointed representatives for the trial)
 - [name] (methodologist)
 - Missions:
 - Define the overall structure of the study, coordinate information, determine the initial methodology and oversee the trial. Propose procedures to be followed during the study. The sponsor (APHP) retains the decision-making authority.

10 SAFETY ASSESSMENT - RISKS AND BURDEN ADDED BY THE STUDY

10.1 Description of Safety endpoints assessment parameters

Safety endpoints will overlap with efficacy (see par 4.1). Coagulation disorders will be specifically monitored, as coagulation might theoretically be affected by the drug, although this effect was not found in safety studies (see investigator brochure).

10.2 Anticipated methods and timetable for measuring, collecting and analysing the safety endpoints

See par 4.1

10.3 Recording and reporting adverse events

10.3.1 Definitions

According to Article R1123-46 of the French Public Health Code:

- **Adverse event**

Any untoward medical occurrence in a trial subject, which does not necessarily have a causal relationship with the clinical trial or with the investigational product.

- **Adverse reaction to an investigational medicinal product**

Any adverse event occurred in a trial subject, which has a causal relationship with the clinical trial or with the investigational medicinal product

- **Serious adverse event or reaction**

Any adverse event or reaction that at any dose of medication, results in death, threatens the life of the research subject, requires hospitalisation or prolongs hospitalisation, causes a severe or long-term disability or handicap, or results in a congenital abnormality or deformity.

- **Unexpected adverse reaction to an investigational medicinal product**

Any adverse reaction to the product, whose nature, severity, frequency or outcome is inconsistent with the safety information described in the Reference Safety Information (summary of product characteristics, or the investigator's brochure if the product is not authorised).

According to Article R.1123-46 of the Code de la Santé Publique and the guidelines for clinical trial sponsors (ANSM):

- **Emerging safety issue**

Any new safety information that may lead to a reassessment of the risk/benefit ratio of the trial or the investigational medicinal product, modifications in the investigational medicinal product use, the conduct of the clinical trial, or the clinical trial documents, or a suspension, interruption or modification of the protocol of the clinical trial or other similar trials.

For the clinical trials involving the first administration or use of an investigational medicinal product in healthy volunteers, any serious adverse reaction.

Examples:

- a) any clinically significant increase in the frequency of an expected serious adverse reaction
- b) suspected unexpected serious adverse reactions in patients who have terminated their participation in the clinical trial that are notified by the investigator to the sponsor together with follow-up reports
- c) any new safety issue relating to the conduct of the clinical trial or the development of the investigational medicinal product, that may impact the safety of the trial subjects.

Examples:

- a serious adverse event likely to be related to the interventions and the trial's diagnostic procedures and which may impact the conduct of the clinical trial,
 - a significant risk on the trial subjects such as ineffectiveness of the investigational medicinal product in treating a life-threatening illness under investigation,
 - significant safety results from a recently completed non-clinical study (such as a carcinogenicity study),
 - the premature termination, or temporary suspension, of a trial conducted on the same investigational medicinal product in another country, for safety reasons,
 - an unexpected serious adverse reaction associated with a non-experimental medication required for the conduct of the clinical trial, (e.g. challenge agents, rescue treatment)
- d) recommendations from the Data Safety Monitoring Board (DSMB), if applicable, that may affect the safety of the trial subjects
 - e) any suspected unexpected serious adverse reaction (SUSAR) reported to the sponsor by another sponsor of a trial carried out in a different country but relating to the same medication.

10.3.2 The role of the investigator

The investigator must **assess the seriousness criteria of each adverse event** and record all serious and non-serious adverse events in the case report form (eCRF)

The investigator must **document** serious adverse events **as thoroughly as possible** and provide a definitive medical diagnosis, if possible.

The investigator must **assess the severity** of the adverse events by using a CTCAE scale:

- or a severity grading scale for adverse events, attached to the protocol

The investigator must assess the **causal relationship** between the serious adverse events and the investigational medicinal product.

The method used by the investigator is based on the WHO Uppsala Monitoring Centre method and uses the following causality terms:

- Certain
- Probable/likely
- Possible
- Unlikely (not ruled out).

These terms are defined as follows (extracted from the WHO-UMC causality categories, version dated 17/04/2012).

Table: WHO-UMC causality categories (extract)

Causality term	Assessment criteria*
Certain	
 · Event or laboratory test abnormality, with plausible time relationship to drug intake ** · Cannot be explained by disease or other drugs · Response to withdrawal plausible (pharmacologically, pathologically) · Event definitive pharmacologically or phenomenologically (i.e. an objective and specific medical disorder or a recognized pharmacological phenomenon) · Rechallenge satisfactory, if necessary
Probable / Likely	
 · Event or laboratory test abnormality, with reasonable time relationship to drug intake** · Unlikely to be attributed to disease or other drugs · Response to withdrawal clinically reasonable · Rechallenge not required
Possible	
 · Event or laboratory test abnormality, with reasonable time relationship to drug intake ** · Could also be explained by disease or other drugs · Information on drug withdrawal may be lacking or unclear
Unlikely	
 · Event or laboratory test abnormality, with a time to drug intake ** that makes a relationship improbable (but not impossible) · Disease or other drugs provide plausible explanations

*All points should be reasonably complied with

** Or study procedures

10.3.2.1 Serious adverse events that require the investigator to notify the sponsor without delay

As per article R.1123-49 of the *Code de la Santé Publique (French Public Health Code)*, the investigator notifies the sponsor without delay (and at the latest within 24 hours) on the day the investigator becomes aware of any serious adverse event which occurs during a study that meets the description in line 1° of Article L.1121-1 of the Code de la Santé Publique, with the exception of any event which is listed in the protocol and, if applicable, in the investigator’s brochure as not requiring notification.

A serious adverse event is any untoward medical occurrence that:

- 1- results in death
- 2- is life-threatening to the participant enrolled in the study
- 3- requires hospitalisation or prolongation of existing hospitalisation
- 4- results in persistent or significant disability/incapacity

It should be noted that the sponsor will particularly monitor the frequency of deaths occurring during the first 5 days (it concerns less than 25 % of the deaths in a prospective cohort of 36 patients meeting criteria for inclusion (18)).

10.3.2.2 Specific features of the protocol

10.3.2.2.1 Other events that require the investigator to notify without delay the sponsor

- Adverse events judged as being "medically significant" not listed in the normal and natural course of the condition (see below)
 - Major bleeding (bleeding necessitating a transfusion of more than 4 packed red blood cells), in the absence of invasive procedure
 - Anaphylactic shock at the time of drug injection
 - Clinical worsening: rescue with VV-ECMO

The investigator must notify the sponsor **without delay (and at the latest within 24 hours) on the day when the investigator becomes aware** of these adverse events, according to the same modalities and within the same timeline as for serious adverse events (see above).

- **In utero exposure**

The investigator must notify the sponsor without delay on the day the investigator becomes aware of any pregnancy that occurs during the study, even if it is not associated with an adverse event.

If the investigational medicinal product is genotoxic, every case of maternal or paternal exposure must be notified.

Notify using a specific form appended to the protocol.

- **Exposure while breastfeeding**

Exposure while breastfeeding occurs if an infant or a child may have been exposed to a medicinal product via the breast milk of a mother being treated with an investigational medicinal product.

Even if it is not associated with an adverse event, the investigator must notify the sponsor without delay on the day the investigator becomes aware of the exposure while breastfeeding.

10.3.2.2.2 Serious adverse events that do not require the investigator to notify the sponsor without delay

These serious adverse events are simply recorded in the case report form. A CRF extraction of these serious adverse events will be realized according to Data Safety Monitoring Board (DSMB) or AP-HP's Safety department's request.

- **Normal and natural course of the condition:**

SARS-CoV-2 induced ARDS is an extremely severe condition, with up to 60% ICU mortality [3]. Moreover, the condition, consisting in severe hypoxia, may affect all organs.

Serious adverse events linked with the condition include particularly:

- Hemodynamic worsening
 - Liver cytolysis/insufficiency
 - Acute renal failure
 - Diffuse intra-vascular coagulation/bleedings
 - Leucopenia/thrombopenia/anemia
 - Severe mesenteric ischemia
 - Brain death/hemorrhagic stroke/ischemic stroke
 - Pulmonary embolism
-

- Acute myocardial infarction/ cardiac rhythm disorders
- Aspiration pneumonia/ ventilator acquired pneumonia/ bacteraemia/fungemia

In this context, those disorders (except deaths) do not need to be notified to the sponsor without delay. A CRF extraction of those serious adverse events will be realized according to a frequency defined in the DSMB charter. A particular monitoring of coagulation tests will be also conducted, to detect any imbalance between groups. These data will be sent to the Data Safety Monitoring Board members and the safety department at [contact]. If there is any imbalance between the randomization groups affecting the safety of trial subjects and which requires the sponsor to take urgent safety measures, the ANSM will be informed about the emerging safety issue without delay.

- ***Adverse events during the trial possibly related with the treatments prescribed as part of the patient's standard care***

The investigator must report these events to his *Centre Régional de Pharmacovigilance (CRPV)*.

10.3.2.3 Period during which SAEs must be notified without delay by the investigator to the sponsor

The investigator notifies the sponsor without delay (and at the latest within 24 hours) of all the serious adverse events listed in the corresponding section:

- starting from the date on which the subject begins treatment with the investigational medicinal product
- throughout the whole follow-up period required for the trial
- until 4 weeks after the end of the subject's treatment with the investigational medicinal product.
- after the end of the clinical trial, if the SAE is likely to be due to the investigational medicinal product (IMP) (e.g. serious reactions that could appear at long term after exposure to the medication, such as cancers or congenital abnormalities) . In that case, the investigator does not have to systematically and indefinitely collect all SAEs possibly related to the IMP, but must notify all possible SAEs related to the IMP of which he has knowledge.

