10.3.3.1 Analysis and declaration of serious adverse events

The sponsor assesses:

- the **seriousness** of all reported adverse events,
- the **causal relationship** between these adverse events and investigational medicinal product and any other treatments,

All serious adverse events for which the investigator and/or the sponsor suspect a causal relationship with the investigational medicinal product are classed as suspected serious adverse reactions.

- the **expectedness assessment** of the serious adverse reactions

Any serious adverse reaction whose nature, severity, frequency or outcome is inconsistent with the safety information described in the investigator's brochure, is considered unexpected.

The sponsor, acting through its safety Department, assesses the expectedness of the serious adverse reaction based on the information described below.

- ❖ For serious adverse events likely to be related to the investigational medicinal product(s):
 - refer to the Investigator's Brochure

- ❖ For the serious adverse events likely to be related to blood samples : malaise, vomiting, pain, hematoma

The sponsor will report all suspected unexpected serious adverse reactions (SUSARs), within the regulatory time frame, to the ANSM (French Health Products Safety Agency)).

- The sponsor must send the initial report without delay upon receipt of the unexpected serious adverse reaction if it is fatal or life-threatening, or otherwise within 15 days from receipt of any other type of unexpected serious adverse reaction;
- The sponsor must provide all relevant additional information by sending follow-up reports, within 8 calendar days following receipt.

Any suspected unexpected serious adverse reaction must also be declared electronically using the Eudragilance European adverse drug reactions database managed by the European Medicines Agency (EMA).

The sponsor must notify all the investigators about any information that could adversely affect the safety of the trial subjects.

Special rules for double blind trials

After unblinding, if the administered product is the investigational medicinal product, the case will be immediately reported as suspected serious unexpected adverse reaction (SUSAR); however, if the administered product is the comparator, the unexpected nature of the adverse reaction will be re-assessed according to the reference document of the comparator found in the protocol.

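### The natural-course exemption from 24-hour SAE notification has no exception for events suspected to be caused by the study drug, and major bleeding falls under both rules

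*Protocol*

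**What the plan says.** Protocol 10.3.2.1 sets the default: the investigator notifies every SAE to the sponsor within 24 hours, unless the protocol or the investigator's brochure lists the event as not requiring it.

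Section 10.3.2.2.2 supplies such a list. It is headed as the natural course of the condition and opens with "Serious adverse events linked with the condition include particularly". Among its entries are "Diffuse intra-vascular coagulation/bleedings", liver cytolysis, leucopenia and cardiac rhythm disorders. For these, "These serious adverse events are simply recorded in the case report form", and "those disorders (except deaths) do not need to be notified to the sponsor without delay". They are extracted from the CRF at a frequency set in the DSMB charter, or when the DSMB or the sponsor's safety department asks.

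Section 10.3.2.2.1 names further events for 24-hour notification. One is "Major bleeding (bleeding necessitating a transfusion of more than 4 packed red blood cells), in the absence of invasive procedure". Another is a catch-all for medically significant events, limited to those that are not on the natural-course list.

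Section 6.4.2 encourages investigators to stop treatment after certain severe events in the "absence of a clear underlying cause other than treatment administration". If treatment is stopped for an SAE, 6.4.3 says "a serious adverse event report will be sent by mail"; 6.4.1 has a similar instruction. Neither gives a deadline.

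Under 10.3.3.1, any SAE that the investigator or the sponsor suspects is drug-related becomes a suspected serious adverse reaction, and "The sponsor will report all suspected unexpected serious adverse reactions (SUSARs), within the regulatory time frame".

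**The concern.** In severe ARDS it is reasonable to spare investigators expedited forms for complications of the disease. The difficulty is that the exemption depends on the name of the event and not on what the investigator thinks caused it. Section 10.3.2 requires the investigator to judge causality for every SAE, but for a listed event type that judgement changes nothing about when the sponsor hears of it.

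The exempt types include those where a drug effect is most plausible on the protocol's own account. Section 10.1 accepts that FX06 could in theory act on coagulation, although the safety studies did not show it, and asks for specific monitoring. Section 6.4.2 treats severe forms of the same event types as possibly drug-caused.

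At stake is prompt single-case assessment of suspected reactions in a phase IIa trial. Major bleeding raises a second problem: an investigator can find it on both lists.

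**Working it through.** No arithmetic decides this point, so the check sets the provisions side by side.

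**Step 1: event types across three lists.**

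| Event type | Exempt list (10.3.2.2.2) | Named for 24-hour notification (10.3.2.2.1) | Severe form on stopping list (6.4.2) |
|---|---|---|---|
| Bleeding | Yes, no severity limit | Yes, if more than 4 packed red cells and no invasive procedure | Yes |
| DIC | Yes | No | Yes |
| Liver cytolysis | Yes | No | Yes |
| Leucopenia | Yes | No | Yes |
| Arrhythmia | Yes | No | Yes |
| Severe allergic reaction | No | Anaphylactic shock only | Yes |

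**Step 2: follow one case.** Take a non-fatal, serious DIC on Day 2 that the investigator rates as probably due to the study drug.

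- 10.3.2.1 requires notification within 24 hours unless the event is listed as exempt. DIC is listed.
- The exemption's one stated exception is death, which does not apply.
- The catch-all in 10.3.2.2.1 covers only unlisted events, so it does not apply.
- 10.3.2.3 has one trigger that depends on drug causality, and it concerns SAEs after the end of the trial. A drug-attributed event learned of after the trial must be notified; the same event on Day 2 need not be.

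The event may therefore be recorded in the CRF only.

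**Step 3: the remaining routes to the sponsor.**

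- CRF extraction, at the charter's frequency or on request by the DSMB or the safety department.
- The reports in 6.4.1 and 6.4.3, which sit in the context of stopped treatment and carry no deadline. They do not help if treatment continues or if the event occurs after the 5-day course. Sections 6.4.1 and 6.4.2 also differ on which events lead to stopping, so how often this route opens is unclear. Those two sections must be reconciled; which of them is right is not judged here.

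**Step 4: effect on SUSAR reporting.** The sponsor's time limits in 10.3.3.1 run from receipt: without delay if fatal or life-threatening, otherwise 15 days. Late receipt moves the whole sequence back.

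**Step 5: major bleeding.** Row one of the table shows it on both lists. The exemption names its exception (death), and the rule on major bleeding is not named as another.

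**Scale of the possible wait.** Inclusions pause for DSMB review at 10 and 30 patients (6.3). At the planned rate of 5 sites × 1.4 per month = 7 patients per month, the two reviews are (30 − 10) / 7 ≈ 2.9 months apart, not counting the pause. No pause is fixed for the last 50 − 30 = 20 patients. This illustrates the fixed reviews only. The charter is not at hand and may set shorter intervals, and the safety department may ask for an extraction at any time.

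**The case against.** The strongest reply is that the list covers events linked with the condition, so an event suspected to be drug-related was never meant to be on it. That may well be the intent. But the operative sentence exempts the disorders by type, and nowhere is the investigator told to notify promptly when the drug is suspected during the trial.

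On major bleeding, the 24-hour rule can be read as a specific rule that overrides a general one, and an investigator who follows it breaches nothing. That is the sensible reading, but the text does not state it.

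Three stronger inferences are tempting, and the protocol does not support them:

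- A reader might infer that the DSMB could resume inclusion without seeing these events. Sections 6.3 and 10.3.4 base each review on a CRF extraction that includes SAEs. Section 10.3.4 adds blood count, coagulation tests and liver enzymes over the first 7 days.
- A reader might infer that the sponsor cannot meet its SUSAR duty. The clock starts at receipt and the safety department can request an extraction, so the duty is delayed, not made impossible or contradicted.
- A reader might count five of the six stopping events as contradicted by the exemption. The stopping list governs treatment, not notification, and presupposes that no cause other than treatment is clear. The count shows shared event types, nothing more.

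**Conclusion.** The concern holds as a defect in the notification rule. Followed to the letter, 10.3.2.2.2 lets a non-fatal SAE of a listed type stay in the CRF until a later extraction even when the investigator suspects the study drug. Four types are plainly affected: DIC, liver cytolysis, leucopenia and arrhythmia. Major bleeding is a separate inconsistency that a reader can probably resolve but should not have to.

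The consequence is delayed individual causality and SUSAR assessment. The data are not lost, and periodic review for imbalance between arms continues. That review does not replace prompt assessment of a single suspected case. The length of the delay is unknown without the DSMB charter. Whether a given reaction would count as unexpected depends on the investigator's brochure, which is also not at hand.

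The conclusion assumes that neither of those documents already restores 24-hour notification for suspected reactions. It is worth correcting because the rule as written gives the worse result, and not merely because detail is missing.

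**What to change.** Reconcile 10.3.2.2.1, 10.3.2.2.2, 6.4.1 and 6.4.3 by adding to 10.3.2.2.2 that the exemption does not apply, and the 24-hour timeline does, when any of these is true:

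- the investigator suspects a causal relationship with the study drug;
- the event is one listed in 10.3.2.2.1;
- the event led to treatment being stopped.

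Sections 6.4.1 and 6.4.3 should then refer to that timeline. Natural-course events with no suspected link to the drug stay exempt, so the purpose of the list is kept.

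This alters reporting only and leaves the criteria for stopping treatment as they are. The cost is a short protocol amendment and a few extra expedited forms in a 50-patient trial.
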